Study Outcomes: The primary outcome will be the extent to which patients and clinicians engage in SDM during the medical encounter following receipt of the intervention or control. Two secondary outcomes include *Patient quality of decision-making process* (knowledge, decisional confidence, self-efficacy, and satisfaction) and *Preference-congruent decision making* to examine whether patient preferences for or against receiving PSA-based screening align with care received (actual receipt of PSA test, extracted from the electronic medical record).

Subjects: 200 African American men, 40-69 years old, with NO diagnostic of prostate cancer, who are receiving primary care (annual physicals and preventive care) at the clinical sites during the project period (2020-2023).

Intervention: Patients will be randomly assigned to receive a 30-45 minute online educational intervention (n=100) or control group (n=100). Patients receiving the training will learn about prostate cancer (risk, screening, diagnoses and treatment), PSA-based screening (benefits, risks, harms, and guidelines), and SDM process (options, perceptions, preferences, actions). In order to measure the application of the SDM process in the clinical setting (primary outcome), patients will discuss the PSA test with their respective primary care provider (PCPs) during a medical wellness visit (annual checkup). The conversation will be audio-recorded, after patient/PCP's assent, and evaluated to identify the application of the different components of the SDM process. If the audio-recording is not authorized, the patient and PCP will complete an evaluation survey about the encounter. Patients will complete online surveys at enrollment (baseline), during the training (pre-post test), and 3-months after medical encounter (follow-up).

Enrollment: Searches in electronic medical records will be conducted to pre-screen and invite (mail, calls, and emails) eligible patients and their respective PCPs to join the study. Patients will complete in-person or online consent and HIPPA authorizations. PCPs' will complete an online baseline survey and provide implicit consent to join the study.

RESEARCH PROTOCOL

Study Title: Fostering Shared Decision-Making about Prostate Cancer Screening among Clinicians and African American men

1. Study aim, background, and design

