Patients and Primary Care Providers (PCPs) medical encounter (Visit #2): In order to measure the application of the SDM process during the clinical setting, patients will discuss the PSA screening with their respective primary care provider (PCP) during a medical wellness visit (annual checkup). Each week, research team will send a reminder (email and/or phone call) to all enrolled patients having scheduled wellness visits in that week, and their respective Primary Care Providers (PCPs).

This visit may be conducted online or face-to-face, as follow:

Online visit: This wellness visit will take place online. The clinical sites have available telehealth services including Zoom videoconference that are HIPPA compliant. An email to schedule the virtual visit (Appendix 1) will be send by Research team to the respective Patient/PCP. Patients who prefer this option will receive instructions on how to proceed. At the beginning of the meeting, the patient and PCP will confirm that they are in a place where privacy may be preserved and that authorize to audio-record the encounter. If the audio-recording is authorized, the research team member will start the recording. If the audio-recording is not authorized or possible, after the encounter the PCP will rate the conversation using the online evaluation form (Physician-Collaborator Patient Evaluation, Appendix 4) and the-patient will complete the online post-encounter surveys (Intention-to-Screen questions, Shared Decision Making Questionnaire, and Decisional Self-efficacy – Appendix 8B). Once the encounter and evaluations are completed the PCP and patients will receive the respective electronic gift card (\$50 and \$40) for the time spent and any expenses incurred during the visit (transportation, parking, Internet and phone services, etc.).

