Face-to-face visit: This wellness visit will take place in the PCP's consultation room at the respective clinical site and will be audio-recorded after patient/PCP's consent. At the beginning of the encounter the research assistant will ask authorization to record the conversation. If the audio-recording is authorized, the research assistant will start the recording. If the audio-recording is not authorized, the research assistant will bring an evaluation form (Physician-Collaborator Patient Evaluation, Appendix 4) for the PCP to rate the conversation. Once the encounter is completed the research assistant will pick up the recorder or the respective evaluation form and will give the PCP a \$50 electronic gift card as appreciation for the time spent. Immediately after the encounter the patient will complete the post-encounter surveys (Intention-to-Screen questions, Shared Decision Making Questionnaire, and Decisional Self-efficacy – Appendix 8B) and will receive a \$40 electronic gift card as compensation for the time spent and any expenses incurred during the visit (transportation, parking, Internet and phone services, etc.).

Follow-up procedures (Visit #3): At 3-months after the medical encounter (visit #2) patients will complete brief post-intervention surveys (Prostate Cancer Knowledge, Decisional Confidence, Satisfaction with Decision, and Intention-to-Screen questions) and an additional questionnaire about the acceptability of the intervention and procedures. These surveys (Appendix 8C) may be completed online or face-to-face, as follow:

- **Online visit:** Research team will send an email (Appendix 1) to participants including a personalized link to the follow-up surveys including contact information in case that participants have questions.
- **Face-to-face visit:** These surveys will be administrated by the research team in a face-to-face meeting that will be scheduled immediately after the medical encounter (visit #2).

After completing the surveys, patients will receive a \$20 electronic gift card as compensation for the time spent and any expenses incurred during the visit (transportation, parking, Internet and phone services, etc.). Additionally, research team will check each year the medical records of each participating patient to see if they have had or not received a new PSA exam during the study period (Jan 2020-Dec 2023).

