Duration: The entire study procedures for each patient may be completed in around six months, including follow-up (Table 1). It is expected that consent and baseline survey (visit #1) will take about 15 to 30 minutes to fill out. Intervention patients will take around 30-45 minutes completing the educational program, including the pre- and post-tests. The PCP/Patient medical encounter (visit #2) will take around 1 hour according to the clinical site schedules and including time needed for patient to complete the respective surveys. Patients' follow-up assessment (visit #3) will take around 15-20 minutes.

Measures and Outcomes. Outcomes will be assessed using different measures (Appendices 4 and 8) and across different post-intervention intervals: immediately after the clinical encounter (visit #2), and at 3-month (± 15 days; visit #3). The primary outcome will be the extent to which patients and clinicians engage in SDM during the patient-clinician encounter (visit #2) following receipt of the intervention or control, evaluated using the Shared Decision Making Questionnaire (SDM-Q). Two secondary outcomes will include: 1) *patient quality of decision-making process*, assessed at baseline (visit #1), immediately after the patient-clinician encounter (visit #2), and at 3-months post intervention (visit #3) using a composite score of the following scales: Prostate Cancer Knowledge, Decisional Confidence, Decisional Self-efficacy, and Satisfaction with Decision, and 2) *Preference-congruent decision making* to examine whether patient preferences for or against receiving PSA-based screening, assessed with Intention-to-Screen questions at baseline (visit #1) and immediately after the clinical encounter (visit #2) align with care received during the subsequent 3 months (physician orders of PSA screening and actual receipt of PSA screen will be extracted from the electronic medical record). The acceptability of intervention and procedures (Tertiary outcome) will be accessed with a structured questionnaire (Appendix 8) to rate the acceptability of the enrollment process, the delivery of the intervention, and their overall satisfaction with the study that patients will complete at the 3-months follow-up (visit #3). Additionally, patients in the intervention arm will complete an evaluation of the educational intervention and the decision aid questions included in the training (Appendix 8D).

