Below is the **Study Design Schema** about the randomization of patients and assessment for both the intervention and the control arms (Figure 1) and the **schedule of activities** and measures to be completed (Table 1).

Figure 1: Study Design Schema

[figure not shown]

Table 1: Study activities and measures to be completed

Visit	Timeline	Procedure	Outcome	Measures
-------	----------	-----------	---------	----------

Visit #1 Consent & Baseline (15-60 min)	After initial contact with patient	Review/sign consent and HIPPA forms		
 • Consent form • HIPPA authorization form
		Complete baseline assessment	Secondary outcome: Patient quality of SDM	
 • Prostate Cancer Knowledge • Decisional Confidence • Satisfaction with Decision • Decisional Self-efficacy
			Secondary outcome: Preference-Congruent DM	
 • Intention-to-Screen questions • PSA screening orders and actual receipt of PSA screen, extracted from the electronic medical record
Intervention (30-45 min)	Before visit #2	Patients in intervention arm: complete training		
 • Prostate Cancer Knowledge • Intention-to-Screen questions • Decision aid questions • Evaluation of training
Visit #2 Medical encounter (approx. 1 hour)	During 3 months after visit #1 and intervention	Complete medical encounter	Primary outcome: Patient and clinicians engagement in SDM	
 • Shared Decision Making-Patient • Shared Decision Making-PCP • Intention-to-Screen questions • Decisional Self-efficacy
Visit #3 Follow-up (15-20 min)	3 months after visit #2	Complete follow-up assessment	Secondary outcome: Patient quality of DM	
 • Prostate Cancer Knowledge • Decisional Confidence • Satisfaction with Decision
			Secondary outcome: Preference-Congruent DM	
 • Intention-to-Screen questions • PSA screening orders and actual receipt of PSA screen, extracted from the electronic medical record
			Tertiary outcome: Acceptability of intervention and procedures	
 • Acceptability of Intervention • Intervention Appropriateness • Feasibility of Intervention

4. Risks

The risks to the patients as participants are minimal.

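### Table 1 lists the clinician-rated SDM measure for Visit #2 without condition, but the procedures collect the clinician's rating only when the encounter is not recorded, so clinician engagement comes from two sources that never overlap

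*Protocol*

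**What the plan says.** **Outcome definition.** Protocol Section 3, Measures and Outcomes, makes the primary outcome the degree to which both patients and clinicians engage in SDM at Visit #2, "evaluated using the Shared Decision Making Questionnaire (SDM-Q"). The same paragraph says that outcome measures are in Appendices 4 (clinicians) and 8 (patients).

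**Schedule.** In Table 1, the Visit #2 row lists a patient SDM measure and "Shared Decision Making-PCP" beside the primary outcome. Neither entry depends on whether the visit was recorded.

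**Procedures.**
- Online visit: "If the audio-recording is not authorized or possible, after the encounter the PCP will rate the conversation using the online evaluation form", the Physician-Collaborator Patient Evaluation in Appendix 4.
- Face-to-face visit: "If the audio-recording is not authorized, the research assistant will bring an evaluation form", the same Appendix 4 form, for the clinician to rate the conversation. Afterwards "the research assistant will pick up the recorder or the respective evaluation form".
- Opening summary, Intervention paragraph: "If the audio-recording is not authorized, the patient and PCP will complete an evaluation survey about the encounter".

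**Recorded encounters.** The same summary paragraph says that the recording is "evaluated to identify the application of the different components of the SDM process" and introduces this as the way to measure the primary outcome. Section 4 (Risks) says that research personnel rate the recordings.

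**Authorisation.** Patients authorise recording in the consent signed at Visit #1 (Sections 3, 4 and 10). Patient and clinician are asked again at the start of the encounter.

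**The concern.** A site that follows the procedures to the letter obtains no clinician rating from a recorded encounter, and recording is the intended default. The clinician measure that Table 1 schedules for Visit #2 would then exist only for the encounters that were not recorded.

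Two things are at stake. First, clinician engagement, which is half of the primary outcome as worded, would come from an observer's rating in some men and from the clinician's own rating in the rest. Because the two are collected as alternatives, no encounter has both, and the trial itself offers no data to relate one to the other. Second, which source a man contributes depends partly on an authorisation reconfirmed after randomisation and, in the intervention arm, after the training. A comparison of arms on clinician ratings alone would be made in a subgroup defined after randomisation and would lose the protection that randomisation gives.

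**Working it through.** The protocol gives no power, effect size or recording rate, so there is no figure of its own to reproduce. The main check is a comparison of sections.

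**Step 1. What each place provides at Visit #2.**

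| Place | Recorded encounter | Unrecorded encounter |
|---|---|---|
| Table 1 | Clinician SDM measure | Clinician SDM measure |
| Section 3, Online visit | No clinician form | Clinician form (refused or not possible) |
| Section 3, Face-to-face visit | No clinician form; recorder collected | Clinician form (refused) |
| Opening summary | Audio evaluated | Patient and clinician survey |
| Section 4 | Audio rated by research personnel | No audio to rate |
| Section 3, Measures and Outcomes | SDM-Q; audio rating not mentioned | SDM-Q |

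The procedures and the summary agree with one another on an either/or rule. Table 1 and the outcome definition do not reflect it.

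**Step 2. Is the either/or rule specific to the clinician form?** In the face-to-face visit it is: the patient surveys follow every encounter, and only the clinician form depends on refusal.

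**Step 3. Is the Appendix 4 form the Table 1 measure?** The protocol names two clinician instruments from Appendix 4: a background survey sent when clinicians are first identified, and the Physician-Collaborator Patient Evaluation. Only the second is used at Visit #2. The match is therefore very likely, but it is an inference because the appendix is not shown.

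**Step 4. How many clinician ratings would exist (illustration).** Inputs: 200 men, 100 per arm (protocol), and an assumed recorded share *r*, equal in both arms.

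Clinician ratings = 200 × (1 − *r*). With *n* = 100 × (1 − *r*) ratings per arm, the detectable standardised difference is (1.960 + 0.842) × √(2/*n*), for two-sided 0.05 and 80% power, with no dropout and no clustering by clinician.

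| Assumed *r* | Ratings | Detectable difference | Power for an assumed 0.5 SD |
|---|---|---|---|
| 0% | 200 | 2.802 × √(2/100) = 0.40 SD | 94% |
| 50% | 200 × 0.50 = 100 | 2.802 × √(2/50) = 0.56 SD | 70% |
| 80% | 200 × 0.20 = 40 | 2.802 × √(2/20) = 0.89 SD | 35% |
| 90% | 200 × 0.10 = 20 | 2.802 × √(2/10) = 1.25 SD | 20% |
| 95% | 200 × 0.05 = 10 | not computed | not computed |

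The 0% row also shows what a form at every visit would give if all 200 men reach Visit #2. The better recording succeeds, the fewer clinician ratings there are.

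**The case against.** The strongest reply is that the either/or rule is deliberate. The summary and both visit descriptions agree on it: record the conversation, and otherwise survey. On this view Table 1 is only a compressed schedule, and adding a condition to one entry and a row for the audio rating would remove the conflict without any change to data collection. It would. That route would still leave clinician engagement measured by two sources with no overlap, in a split settled partly after randomisation.

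A reader might infer that the clinician side of the primary outcome is missing altogether for recorded encounters. The documents do not support that. Those encounters yield an audio rating that the summary ties to the primary outcome. What they lack is the clinician's own rating.

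A reader might also infer that refusals will be common or will differ by arm. Nothing in the protocol says so, and patients have already authorised recording once at enrolment, which makes later refusal by patients less likely. The dependence on a post-randomisation step remains, because both parties are asked again at the encounter and, online, recording may also prove impossible.

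Nor do the documents show that the two sources cannot be combined. The audio-rating instrument is not described and Appendix 4 is not shown, so comparability cannot be judged either way.

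The procedures use the SDM-Q name only for a patient survey, and Table 1 places some secondary measures in the same Visit #2 cell. The clinician form's status as a primary measure is therefore plausible rather than explicit.

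Finally, a combination rule could properly sit in a statistical analysis plan that is not shown. But no analysis plan can recover ratings that clinicians were never asked to give, and Section 4 has the audio files deleted six months after the encounter.

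**Conclusion.** The contradiction stands and should be fixed. Table 1 schedules a clinician SDM measure at Visit #2 without condition, while the procedures obtain the clinician's rating only from unrecorded encounters: refused face-to-face, refused or not possible online. Recorded encounters have an audio rating that the outcome definition and Table 1 leave out.

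The size depends on a recording rate that the protocol does not state. Over an assumed 50% to 95% recorded, 100 down to 10 of 200 clinician ratings would remain. These figures illustrate the mechanism and do not forecast it. The conclusion also assumes that the Appendix 4 form is the measure named in Table 1. It does not rest on any difference in refusal between arms.

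This falls short of a fatal flaw, because clinician engagement is still observed in recorded encounters and the patient measure is a separate component.

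**What to change.** 1. In the opening summary and in both visit descriptions in Section 3, have the clinician complete the existing Appendix 4 form after every Visit #2 encounter, recorded or not. In the face-to-face text, have the assistant collect both the recorder and the form. One clinician measure would then be planned for all men, as Table 1 lists it.
2. In Measures and Outcomes and in Table 1, state which source is the primary clinician measure, and confirm that the Appendix 4 form is the measure Table 1 names.
3. List the audio rating in both places as a separate measure for recorded encounters rather than a substitute. Encounters with both would also allow the two to be compared.
4. Reconcile the payment wording. Section 6 ties the clinician's $50 to recorded encounters, whereas the Section 3 visit descriptions pay it for the encounter whether or not it was recorded.

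The cost is an amendment to wording and a few minutes of clinician time per recorded visit. The form exists, and all three payment passages already cover recorded encounters, which are the ones where the extra forms would arise.

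### The four-scale composite secondary outcome cannot be formed as defined at either post-baseline visit, because the outcome definition and the visit schedule disagree

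*Protocol*

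**What the plan says.** The protocol's opening summary (Study Outcomes) lists four components for this secondary outcome: "knowledge, decisional confidence, self-efficacy, and satisfaction". Section 3, Measures and Outcomes, repeats them as a score formed "using a composite score of the following scales: Prostate Cancer Knowledge, Decisional Confidence, Decisional Self-efficacy, and Satisfaction with Decision", and gives its timing as "assessed at baseline (visit #1), immediately after the patient-clinician encounter (visit #2), and at 3-months post intervention (visit #3").

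The visit descriptions in the same section list the surveys patients receive:

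- Visit #2, the medical encounter: "post-encounter surveys (Intention-to-Screen questions, Shared Decision Making Questionnaire, and Decisional Self-efficacy"). The online and face-to-face descriptions name the same three instruments.
- Visit #3, the follow-up: "brief post-intervention surveys (Prostate Cancer Knowledge, Decisional Confidence, Satisfaction with Decision, and Intention-to-Screen questions"), plus an acceptability questionnaire.

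Table 1 lists all four scales at Visit #1 and otherwise agrees with the visit descriptions. It labels Visit #2 with the primary outcome, "Patient and clinicians engagement in SDM", and places "Patient quality of DM" at Visit #3. The window for the last visit is "and at 3-month (± 15 days; visit #3").

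**The concern.** A composite has to be built from its components. If a component is not administered at a visit, the score as defined does not exist there. This is one of only two secondary outcomes, and on the schedule as written it is complete only at baseline, before the intervention can have acted.

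The team would then have to choose, possibly after data collection, between a three-scale score, a score pieced together across two visits, and separate scales. That is avoidable discretion over a prespecified outcome. A like-for-like change from the four-scale baseline would be available only through the pieced-together score, and there would be no repeated post-baseline composite to model.

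**Working it through.** The protocol gives no figure to reproduce here. The check sets the four component scales against the instruments scheduled at each visit. Visit #1 is taken from Table 1. Visits #2 and #3 are taken from both the visit descriptions and Table 1, which agree.

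| Scale | Visit #1 | Visit #2 | Visit #3 |
|---|---|---|---|
| Prostate Cancer Knowledge | yes | no | yes |
| Decisional Confidence | yes | no | yes |
| Satisfaction with Decision | yes | no | yes |
| Decisional Self-efficacy | yes | yes | no |
| **Scheduled** | **4 of 4** | **1 of 4** | **3 of 4** |

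1. Implied by the outcome definition: 4 scales × 3 visits = 12. Scheduled: 4 + 1 + 3 = 8. Missing: 3 at Visit #2 and 1 at Visit #3, total 4.
2. After baseline: implied 4 × 2 = 8; scheduled 1 + 3 = 4.
3. Four-scale composites at a single post-baseline visit: 2 named, 0 possible.
4. Visits #2 and #3 taken together: 1 + 3 = 4 scales with no overlap, so at most one across-visit score. Counting Visit #3 from Visit #2, as the follow-up procedures and Table 1 do, and taking 3 months as 90 days, its parts would lie 90 − 15 = 75 to 90 + 15 = 105 days apart. At baseline all four are taken at one visit.
5. On Table 1's own assignment of this outcome (Visits #1 and #3): implied 4 × 2 = 8; scheduled 4 + 3 = 7. The one missing is Self-efficacy at Visit #3.

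The Knowledge survey given with the training does not close the gap. It goes to the intervention arm only and comes before Visit #2. Broken table extraction is not the explanation either, because the running text and Table 1 agree for Visits #2 and #3, and both conflict with the outcome definition.

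**The case against.** The strongest reply is that the definition never says each scale is given, or a separate score computed, at every visit. It speaks of different measures over different intervals. The four scales also split exactly between Visits #2 and #3, which would fit a single post-baseline composite assembled from both. Scoring is commonly left to the analysis plan, which is not shown here. On that reading the fault is ambiguity rather than impossibility.

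Part of this stands. An across-visit score is possible, and an analysis plan could define one. But the protocol describes no such score, and it would yield one post-baseline value where the plain reading of the definition gives two. If it was intended, the definition still has to be rewritten. No analysis plan can supply a same-visit score that needs Self-efficacy at Visit #3.

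It is also fair to say that on Table 1's assignment the gap shrinks to one scale at one visit, with a stray mention of Visit #2. And the hypothesis in section 1 is a between-arm comparison that names decision confidence and satisfaction, both collected at Visits #1 and #3. These points limit the consequence without removing the contradiction.

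**Conclusion.** The concern holds. The composite can be formed as defined at baseline only; it cannot be formed at Visit #2 or at Visit #3 taken singly. The shortfall is 4 of the 8 post-baseline measurements on the definition's timing, or 1 of 8 overall on Table 1's.

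This should be fixed, but the damage is limited. The individual scales can still be compared between arms, the confidence and satisfaction hypothesis remains testable at Visit #3, and this mismatch does not touch the primary outcome. The conclusion assumes that the survey forms in Appendix 8, which are not shown, contain what the visit descriptions and Table 1 say they contain.

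**What to change.** 1. In Measures and Outcomes, remove Visit #2 from the composite's assessment times, so that it matches Table 1.
2. Add the existing Decisional Self-efficacy scale to the Visit #3 survey (follow-up procedures, Appendix 8C, Table 1). Scheduling then becomes 8 of 8 at Visits #1 and #3.
3. Keep Self-efficacy at Visit #2 and report it separately.

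If any patient has already passed Visit #3 when the amendment takes effect, define the composite at Visits #1 and #3 on the three scales common to both, so that it means the same thing for every patient. This drops self-efficacy, so the component lists in Study Outcomes and in Measures and Outcomes must be amended to match. The across-visit score would keep all four components, but at the price of mixing times about three months apart.

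One separate wording point can go into the same amendment. The online Visit #2 text can be read as giving patients the Appendix 8B surveys only when recording is refused or not possible. The summary's Intervention paragraph has a looser sentence to similar effect, and its list of patient survey times omits Visit #2. The face-to-face text, the Duration paragraph and Table 1 point the other way. Reword so that all patients complete Appendix 8B whether or not the encounter is recorded. The main finding does not depend on this.

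The cost is one existing scale added to a 15–20 minute visit, plus text changes, all in one IRB amendment. Scoring and model details can stay with the analysis plan.

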- For those completing the visit face-to-face, and based on participant preferences and time and transportation constraints, the meeting could be scheduled at the private offices of research personnel, at the respective clinic, or in a specific place chosen by the patient where privacy may be preserved. In this case, the consent (Appendix 6A) and HIPPA (Appendix 7A) forms will be completed on paper and signed copies will be given to participants to keep.
- For those completing the visit online, the consent will be presented on a set of questions and short answers extracted from the consent form (Appendix 6B) and a link to the entire consent will be available so participants can read and save the entire document before continuing with the consent process. The online consent requires electronic signature for the consent and HIPPA (Appendix 7B) authorization. Patients can sign the documents by signing their name using the finger, mouse or stylus pen.

After completing the consent, surveys and training, patients will receive a \$40 electronic gift card as compensation for the time spent and any expenses incurred during the visit (transportation, parking, Internet and phone services, etc.)

Educational intervention procedures (online training): Patients randomly assigned to the intervention arm will complete an online educational program (Appendix 9) to enhance knowledge about prostate cancer and risks, and application of shared decision making (SDM) skills. Patients will complete the training immediately after enrollment and baseline (Visit #1). Research team will send an email (Appendix 1) to participants including a personalized link to the training and respective surveys (Prostate Cancer Knowledge, Intention-to-Screen questions, Evaluation of Training and Decision Aid Questions, Appendix 8D), and

contact information in case that participants have questions or need help to navigate the site. Patients in the control arm will be given instructions to complete the training once the entire study procedures are completed (6-months after enrollment).

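### The online-visit text and the record-extraction limit contradict the outcome definitions: recorded online visits get no Visit #2 patient surveys, and PSA orders are left out of the extraction

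*Protocol*

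**What the plan says.** **Outcome definitions.** Section 3, Measures and Outcomes, assesses the primary outcome at Visit #2 with the SDM Questionnaire. It defines the second secondary outcome by whether "Intention-to-Screen questions at baseline (visit #1) and immediately after the clinical encounter (visit #2) align with care received during the subsequent 3 months", with physician orders and actual receipt both taken from the electronic record. Table 1 lists Intention-to-Screen, the patient SDM measure and Decisional Self-efficacy at Visit #2 with no condition attached. At Visits #1 and #3 it lists "PSA screening orders and actual receipt of PSA screen, extracted from the electronic medical record".

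**Visit #2 procedures.** For online visits, one sentence opens with "If the audio-recording is not authorized or possible, after the encounter the PCP will rate the conversation using the online evaluation form" and goes on to say that "the-patient will complete the online post-encounter surveys (Intention-to-Screen questions, Shared Decision Making Questionnaire, and Decisional Self-efficacy" will follow. For face-to-face visits, the PCP form depends on recording being refused, but the patient surveys do not: "Immediately after the encounter the patient will complete the post-encounter surveys (Intention-to-Screen questions, Shared Decision Making Questionnaire, and Decisional Self-efficacy".

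**Synopsis.** The Intervention paragraph gives the survey times as "Patients will complete online surveys at enrollment (baseline), during the training (pre-post test), and 3-months after medical encounter (follow-up", with no routine Visit #2 survey. It adds: "If the audio-recording is not authorized, the patient and PCP will complete an evaluation survey about the encounter". The Study Outcomes paragraph describes care received as receipt of the PSA test and does not name orders.

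**Record data.** Section 4, Procedures to minimize identified risks, says that contact details and a yes/no item on PSA screening are the only things extracted from the medical record. It repeats that item when it describes the control sheets.

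**The concern.** Staff follow the visit procedures and the confidentiality text, and here both are narrower than the outcome definitions.

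If the online instruction is followed literally, a man seen online and recorded answers none of the three Visit #2 instruments. His preference after the encounter is then unknown, and the patient-reported primary measure is missing. Decisional Self-efficacy is missing too, and Table 1 schedules it at no later visit. Completeness would depend on visit mode and on whether recording took place, both settled after randomisation. An analysis plan can handle missing answers but cannot recover questions that were not asked.

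If the extraction limit is followed literally, orders may not be taken from the record, so the order part of the congruence outcome has no permitted source.

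**Working it through.** The protocol states no figure to reproduce, so the check is a comparison of texts.

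**Step 1. Visit #2 patient surveys, by visit type.** Measures and Outcomes and Table 1 require them in every row.

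| Visit #2 | Recorded | Patient surveys under the visit paragraph |
|---|---|---|
| Face-to-face | Yes | Given |
| Face-to-face | No | Given |
| Online | No | Given |
| Online | Yes | Not provided for |

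One cell of four fails. The synopsis supports the literal reading of the online paragraph, because it too ties an encounter survey to the absence of a recording. It is not decisive: taken at face value it would also remove the survey from recorded face-to-face visits, which the face-to-face paragraph contradicts.

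**Step 2. Can another source fill that cell?**

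- Baseline intention exists for everyone, but it precedes the training: "Patients will complete the training immediately after enrollment and baseline (Visit #1".
- The intention asked with the training exists in the intervention arm only (Table 1).
- Visit #3 intention is asked three months after the encounter, when the care window closes.
- The recording is rated by research personnel for SDM and deleted six months after the encounter (Section 4). A rater's score is not the patient's own questionnaire, and the protocol does not say that intention will be coded from the recording.

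None of these is the preference stated immediately after the encounter.

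**Step 3. Record data, place by place.**

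| Place in protocol | Orders | Receipt | Timing |
|---|---|---|---|
| Measures and Outcomes | Yes | Yes | 3 months after the encounter |
| Table 1, Visits #1 and #3 | Yes | Yes | At those visits |
| Synopsis, Study Outcomes | Not named | Yes | None given |
| Follow-up procedures, yearly check | Not named | New exam, yes/no | Jan 2020-Dec 2023 |
| Section 4, extraction limit | Excluded by its wording | Yes/no | None given |
| Section 4, control sheets | Not listed | Yes/no | None given |

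The first two rows and the extraction limit cannot all hold. No place provides for the date of an order or a test, although the outcome is judged over three months.

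**Step 4. Size.** The men affected under Step 1 are those among the 200 whose Visit #2 is both online and recorded. The protocol gives neither the online share nor the recorded share, so the number cannot be calculated.

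**The case against.** The strongest reply is that the online sentence is clumsy drafting and not a different design. Payment at online visits follows completion of the encounter and the evaluations by both PCP and patient. The Duration paragraph allows about an hour for Visit #2 and counts the patient's survey time in it, whatever the mode. The online option was added in Version 2, which may explain a badly joined sentence. All this stands as evidence of intent. It does not change the instruction, which remains conditional and agrees with the synopsis.

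Some stronger conclusions are tempting, but the protocol does not support them:

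- *The Visit #2 preference is missing throughout.* It is provided for at all face-to-face visits and at unrecorded online visits.
- *Affected men drop out of the congruence outcome.* The definition also uses the baseline preference, so that version can still be scored for them.
- *PSA orders are not collected.* Measures and Outcomes and Table 1 say that they are. This is a contradiction, not an omission.
- *PSA receipt cannot be placed in the three-month window.* Table 1 puts the record extraction at Visit #3, so whoever reads the record could apply the window and store a yes/no result. The yearly check is introduced as an addition and is not the stated source. Record data can also be re-read later if the authorisation allows. The need for dates is therefore an inference.
- *Precision or power falls by a stated amount.* That would need shares and congruence rates that the protocol does not give.

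Which preference takes priority in scoring, and whether orders and receipt are reported separately, are matters for the SAP and are not criticised here.

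**Conclusion.** The point holds as two contradictions within the protocol.

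1. As written, the online-visit paragraph leaves recorded online visits without the Visit #2 intention, the patient SDM Questionnaire and Decisional Self-efficacy, against the face-to-face paragraph, Measures and Outcomes and Table 1. This is the more serious of the two, because it touches the primary-outcome measure and the loss would be permanent.
2. The extraction limit in Section 4 conflicts with the extraction of PSA orders that Measures and Outcomes and Table 1 require.

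The size of the first is unknown: zero if no visit is online or if sites survey everyone, and otherwise equal to the number of recorded online visits at which the text is followed literally. The conclusion rests on the protocol body. Appendices 4, 7 and 8 are not shown and could clarify practice, but they would not remove the conflict in the text. The correction should be made; confidence is medium because the gap was probably not intended.

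**What to change.** **Online-visit paragraph, Section 3.** Separate the patient surveys from the recording condition, for example: *The patient fills in the Appendix 8B surveys online after the encounter, whether or not it was recorded.* Leave the condition on the PCP form as it is.

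**Synopsis.** Add Visit #2 to the patient survey times, and name PSA orders with receipt under Study Outcomes.

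**Section 4, extraction limit and control sheets.** Replace the yes/no item with PSA orders and PSA receipt, to match Measures and Outcomes and Table 1. Preferably add their dates, so that the three-month window can be verified. First check that the HIPAA authorisation (Appendix 7) covers these items.

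**Cost.** An IRB wording amendment, one short survey at recorded online visits, and slightly more record data held per patient.
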